**C. Hypotheses:**

a. Patients randomized to KIOS- Bipolar compared with those randomized to eMoods will have a higher proportion of time in remitted status, lower proportion in syndromal status (Manic, depressed, mixed) and higher

LFQ scores.

- b. Persistence with use of KIOS- Bipolar and eMoods will not differ. Persistence is defined as 1) the proportion of subjects who complete weekly scheduled use of the bipolar self-assessment scales and 2) completion of the 52 week self-assessment protocol.
- c. The proportion of on-time completion of assessments will not differ between groups.
- d. Subject satisfaction, assessed by qualitative questionnaires completed by subjects during and principally shortly following completion or discontinuation of the trial, will not differ between groups.
- e. LFQ subscales will be associated with superior outcomes for the KIOS-Bipolar group.
- f. Correlations between scores on items included in KIOS- Bipolar and similar items on the BISS SR and the BISS 42 will be conducted. Strength of association will be higher between KIOS- Bipolar and BISS comparisons than eMoods-BISS comparisons.
- g. Aggregate changes for the KIOS- Bipolar items and corresponding eMoods items will indicate greater proportions of decreased scores for KIOS- Bipolar

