#### **ASSESS KIOS-BIPOLAR OR eMOODS:**

- a. At the beginning of the study subjects will be provided preformatted evaluation sheets and will be encouraged to note observations regarding ease/benefits of use, impediments to use, and suggestions for additional features that would enhance the utility of KIOS-Bipolar or eMoods for sustained health.
- b. We will ask the subjects to estimate how completing the KIOS-Bipolar /eMoods assessments contributed to their self-awareness, attitude, and overall sense of satisfaction with their health status.
- c. We will assess the sensitivity of KIOS-Bipolar to identify improving or worsening by comparing the concordance between subject-assessed items with staff -administered BISS items that address similar symptoms.

**Plan of analysis:** The primary aims of the analyses are to investigate patterns of adherence and attrition. The term adherence refers to the extent to which participants follow the weekly completion of KIOS-Bipolar's eight pivotal symptoms of bipolar disorder. Adherence will be measured through such usage indicators as the proportion of weeks completed on time, the proportion completed only with follow-up prompts, and the number of weeks not submitted. Proportions of stable trajectories or improving trajectories are of primary interest. With  $n=90$  subjects (which allows for as many as 30 of the enrolled 120 subjects to have met some criterion for early termination) in the study we will be able to estimate any proportion within 0.10 with 95% confidence. For proportions larger than 0.9 we will be 95% confident we are within 0.06 of the true proportion. For a trajectory neither improving nor degrading there should be a 0.5 proportion

UTHSCSA tracking number: HSC20150321H

of each. For any hypothesis test for a proportion improving or degrading, i.e. not 0.5, we have 0.80 power at two tail significance of 0.05 to detect 0.65 different from 0.5 with n=90 subjects. For subgroups of patients with n=45 we can detect 0.71 different from 0.5 and with n=30 we can detect 0.74 different from 0.5. When comparing proportions of two subgroups of subjects, we will be 95% confident that the difference in proportions of the two subgroups is less than 0.25 for subgroups of n=30 and smaller than 0.20 for subgroups of size 40. If the proportions are larger than 0.9 (i.e. less variable), then we will be 95% confident that the difference in proportions of two subgroups with n=30(45) is less than 0.15 (0.12).

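### Adherence, a primary aim of the analysis, is defined on KIOS-Bipolar entries only, but its 0.10 precision is stated for 90 subjects counted across both arms

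*Combined protocol and SAP*

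**What the plan says.** In the Plan of analysis (under ASSESS KIOS-BIPOLAR OR eMOODS), "The primary aims of the analyses are to investigate patterns of adherence and attrition". The definition follows: "The term adherence refers to the extent to which participants follow the weekly completion of" the KIOS-Bipolar items, in full "weekly completion of KIOS-Bipolar's eight pivotal symptoms of bipolar disorder", and eMoods is not named in that definition. It is to be measured by the share of weeks entered on schedule, the share entered only after a reminder, and the count of missing weeks.

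The same paragraph sets n=90, "which allows for as many as 30 of the enrolled 120 subjects to have met some criterion for early termination", and states that with this number "we will be able to estimate any proportion within 0.10 with 95% confidence". For proportions above 0.9 it gives 0.06.

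For two subgroups it gives a margin below 0.25 with 30 each and below 0.20 with 40 each. For proportions above 0.9 the margins are 0.15 with 30 each and 0.12 with 45 each. None of these is labelled as the comparison of the two arms.

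Other sections treat completion as an outcome in both arms. Objective b in the list of trial objectives covers weekly completion of both tools. Hypothesis b in section C reads "Persistence with use of KIOS- Bipolar and eMoods will not differ", and hypothesis c makes the same prediction for on-time completion.

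**The concern.** The definition and the denominator do not belong together. Subjects assigned to eMoods do not fill in the KIOS-Bipolar items, so the measure as defined cannot have 90 contributors when 90 is the number left in both arms. The precision printed beside the definition is therefore better than the measure can deliver.

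The definition also departs from the objectives and hypotheses. An analyst who followed the Plan of analysis literally would derive the usage indicators in one arm only, whereas hypotheses b and c need them in both. Those hypotheses predict no difference between the arms, so the between-arm margin decides how much a small observed difference can support, and the plan does not state it.

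**Working it through.** **Inputs.** Enrolled 120 (section B); allowance for loss 30, leaving 90 (Plan of analysis). No allocation ratio is given. Assuming 1:1, there are 120/2 = 60 randomised and 90/2 = 45 retained per arm.

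**The plan's own figures at n=90.** The 95% half-width is 1.96 × sqrt(p(1−p)/n).
- p=0.5: 1.96 × sqrt(0.25/90) = 0.103, stated as 0.10. A strict 0.10 needs 1.96² × 0.25/0.10² = 96.04, that is 97 subjects.
- p=0.9: 1.96 × sqrt(0.09/90) = 0.062, stated as 0.06.

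Both reproduce to rounding, so the formula is sound for 90 contributors.

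**Same formula for adherence as defined (KIOS-Bipolar arm only).**
- 45 retained, p=0.5: 1.96 × sqrt(0.25/45) = 0.146.
- 45 retained, p=0.9: 1.96 × sqrt(0.09/45) = 0.088.
- All 60, no loss, p=0.5: 1.96 × sqrt(0.25/60) = 0.1265.
- All 60, no loss, p=0.9: 1.96 × sqrt(0.09/60) = 0.076.

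The stated 0.10 and 0.06 are missed in both cases.

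**Between-arm margin.** For two groups of n each at p=0.5, the half-width is 1.96 × sqrt(2 × 0.25/n).
- n=30: 0.253, stated as below 0.25; agrees to rounding.
- n=40: 1.96 × sqrt(0.5/40) = 0.219, stated as below 0.20. Reaching 0.20 needs 1.96² × 0.5/0.20² = 48.02, that is 49 per group.
- n=45: 1.96 × sqrt(0.5/45) = 0.207.
- n=60: 1.96 × sqrt(0.5/60) = 0.179.

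At 45 per arm and p=0.9 the margin is 1.96 × sqrt(0.18/45) = 0.124, in line with the printed 0.12.

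**Trajectory test.** The approximate power to detect p against 0.5 is Φ[(p − 0.5 − 1.96 × sqrt(0.25/n)) / sqrt(p(1−p)/n)]. For p=0.65 and n=90 this is Φ[(0.15 − 0.1033)/0.0503] = 0.82. Across normal, continuity-corrected, arcsine and exact versions, the proportion detectable with 80% power is 0.646 to 0.651 at n=90 (stated 0.65) and 0.703 to 0.714 at n=45 (stated 0.71). Both figures reproduce.

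**The case against.** **The definition may be loose wording.** The section heading names both tools, objective b covers both, and Table 1 schedules both on the same row. Read that way, a pooled n=90 gives the stated precision to rounding. That is a fair account of what was probably intended, but it is not what the definition says. It also leaves hypotheses b and c without a margin, because they compare arms and do not pool them.

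**The 0.146 is a ceiling.** This stands. It assumes 1:1 allocation, loss of all 30, and p=0.5. A yes/no measure with 45 subjects is within 0.10 once the proportion reaches about 0.865. If adherence is averaged as a per-subject fraction of weeks, the half-width is 1.96 × SD/sqrt(45), which is within 0.10 when the SD is at most 0.10 × sqrt(45)/1.96 = 0.34; the documents give no SD. Subjects who leave early still supply weeks until they go. But the plan claims its 0.10 for any proportion, so the worst case is the fair comparison, and even 60 subjects do not reach it.

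**A reader might infer that the detectable proportion of 0.65 falls too.** The documents do not support this. The figure "to detect 0.65 different from 0.5 with n=90 subjects" is given for trajectories that improve or degrade, not for adherence. The BISS is scheduled for all subjects, and hypothesis g pairs KIOS-Bipolar items with eMoods items, so a pooled trajectory test is possible. The plan does not name the instrument that defines a trajectory. Only if that is KIOS-Bipolar alone does its own 0.71 for n=45 apply instead.

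**A reader might also infer that eMoods adherence is not measured.** It is. eMoods entries are scheduled weekly and reach the coordinator by email or at visits, and hypothesis b carries its own definition of persistence for both tools. The fault is an inconsistent definition, not missing data.

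**Conclusion.** The point holds as a mismatch between definition and denominator. For adherence as defined, the worst-case 95% margin is 0.146 with 45 retained or 0.1265 with all 60, against a stated 0.10. At p=0.9 with 45 it is 0.088, against 0.06. The definition also contradicts objective b and hypotheses b and c.

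For the comparison that those hypotheses need, the worst-case margin at 45 per arm is 0.207. The printed bound of 0.20 for groups of 40 is not a safe substitute, since the figure there is 0.219 at p=0.5.

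The n=90 arithmetic is correct for analyses that pool both arms. The per-arm figures rest on an assumed 1:1 ratio. The option to switch tools after technical difficulty (Software, section D) means that the number using KIOS-Bipolar may differ from the number randomised to it.

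**What to change.** - Define adherence as weekly completion of the assigned tool, KIOS-Bipolar or eMoods, with the same three usage indicators in each arm. Say how subjects who switch tools are counted.
- State the allocation ratio. If it is 1:1, give a worst-case precision of about 0.15 per arm at n=45 and a between-arm margin of about 0.21 at 45 per arm, and do not rely on the 0.20 printed for groups of 40.
- Keep the n=90 precision figures only for analyses that pool the arms, and label them so.
- Name the instrument that defines a trajectory and the arms that the 0.65 covers. If it is KIOS-Bipolar alone, use the 0.71 already printed for n=45.

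The cost is a few sentences and less favourable printed figures. No extra data and no change in sample size are needed.

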## **Comparative Effectiveness of Two Self-Assessment Tools: KIOS-Bipolar or eMoods: A Randomized, Open 52 Week Study for Persons with Bipolar Disorder**

**[name], [name], [name], [name], [name], [name].**

### **Abstract/Project Summary**

#### **A. Objective: *What we propose to do***

Bipolar disorder (BD) is a complex chronic illness characterized by recurrent, often dramatic mood changes. Self-management of BD is an important component of treatment, but is likewise complex and can be fraught with difficulties, including misunderstanding of the condition and a lack of self-awareness. Combined with the nationwide shortage of mental healthcare providers and the advent of the Affordable Healthcare Act, patients are assuming an increased role in understanding and managing their chronic conditions. At the same time, the emergence of mobile health and computational tools are engaging patients in self-management by enabling timely access to information and resources.

The goal of this project is to complete the development of a patient-centered software system and mobile app to assist in managing bipolar disorder. In Phase I, we developed a novel computational tool known as KIOS-Bipolar. Based on concepts from nonlinear systems (chaos) theory, KIOS-Bipolar tracks multiple interacting symptoms to determine the precise state of a BD patient. Once the patient's state is identified and the trajectory of the patient is established, KIOS-Bipolar produces advice specific to the patient's condition to help manage the course of the disease. To facilitate user convenience for the software, KIOS-Bipolar was converted to an online tool with mobile access. Twenty bipolar patients evaluated KIOS-Bipolar in a twelve week field trial. No technical problems with the software were observed and results showed that patients had significantly more reductions in symptom severity than increases. The development of this innovative tool to help patients self-manage BD has the potential to profoundly impact public health and achieve significant commercial success.

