Assumptions needed for each analysis will be examined to assure they are reasonably well met and the conclusions are valid. End of study overall improvement or not for each measure can be analyzed with logistic regression using covariates and predictors of interest. By focusing analyses on proportions and changes in trajectories, each subject will serve as their own control and trends in improved scores, symptoms and behavior may be identified.

Initially, we will also assess the effects of site, ethnicity, and bipolar disorder subtype (BD I, BD II), but none of these factors will be retained in the final model if they are not shown to be significant moderating factors.

The rate of dropout at any given time will be modeled through logistic regression models, with health, socioeconomic, and treatment factors as explanatory variables. *The impact of quality of life on dropout will be assessed similarly.*

**Outcome Measures from KIOS Analytics:** Knowledge Base performance metrics will be computed to measure the effectiveness of the content provided to patients. These metrics take several forms and are based on changes in the symptom scores for all subjects in the field trial (see Phase I Final Report). Changes in the symptom scores provide a global measure of efficacy. Each of these measures can be computed as a function of changes, either over the course of the entire field trial or at each incremental assessment. This latter approach will provide a measure of effectiveness over time. Other KIOS analytic methods will reveal which specific content in the knowledge base needs improvement. Behavioral frequency analysis will show which patient states are entered most frequently. Behavioral transition analysis will show which conditions are precedents to undesirable states.

**Implementation of Clinical Trial Results into Final Product:** The results of the randomized trial will be used to make further refinements to KIOS-Bipolar. The KIOS-generated results will be used to guide changes to the knowledge base. Suggestions about additional features will be considered in development of the commercialization plans.

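### The 0.5 reference for trajectories has no place for stable subjects, so either the null value or the stated power is wrong once any subject is stable

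*Combined protocol and SAP*

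**What the plan says.** The Plan of analysis (under ASSESS KIOS-BIPOLAR OR eMOODS) gives adherence and attrition as the main aims, then adds: "Proportions of stable trajectories or improving trajectories are of primary interest". A precision statement follows for 90 subjects, which is what remains if 30 of the 120 enrolled leave early.

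The no-change reference comes next: "For a trajectory neither improving nor degrading there should be a 0.5 proportion". The sentence finishes after a page footer and applies the 0.5 to each of the two directions.

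The power statement opens: "For any hypothesis test for a proportion improving or degrading, i.e. not 0.5". With a two-sided level of 0.05 and 90 subjects, it claims power of 0.80 when the true value is 0.65. For subgroups of 45 and 30 the detectable values are given as 0.71 and 0.74. The following paragraph says that, with this focus, "each subject will serve as their own control".

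Section C (Hypotheses) separately states comparisons of KIOS-Bipolar with eMoods, including time in remission, LFQ scores and the proportion of decreased item scores. The Plan of analysis gives confidence-interval widths for a difference between two subgroups, but no power for comparing the arms.

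**The concern.** Half improving plus half degrading makes the whole sample. The category that the plan has just called of primary interest, stable, has no share under this null. The plan does not define stable, gives no expected frequency for it, and does not say where stable subjects are counted.

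Stable subjects are to be expected. The inclusion criteria require at least four weeks on a mood stabiliser or second-generation antipsychotic and set no minimum symptom level, and remission is one of the seven states to be counted.

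What is at stake is the meaning of the plan's only stated power calculation. Depending on how stable subjects are handled, the test rejects too often in one direction, rejects too often in the other, or has less power than claimed.

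There is also a separate problem of attribution. The 90 subjects come from both arms, so a within-subject test on them cannot separate an app effect from illness course or ongoing treatment.

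**Working it through.** **Inputs.** From the Plan of analysis: n=90 (and 45 for a subgroup), reference 0.5, alternative 0.65, two-sided 0.05, power 0.80. Assumed, because the documents give no figure: a stable share s of 10%, 20% or 30%, with improvement and worsening equally likely when the app has no effect, so each has probability (1−s)/2.

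**Step 1: reproduce the stated power.** The exact binomial test at n=90 rejects at 55 or more, or 35 or fewer (actual size 0.045). At p=0.65 its power is 0.81. The normal approximation gives z = (√90 × 0.15 − 1.96 × 0.5)/√(0.65 × 0.35) = (1.423 − 0.980)/0.477 = 0.93, so power 0.82. For 0.71 at n=45, power is 0.79 exact and 0.83 normal. For 0.74 at n=30, it is 0.77 exact and 0.78 normal. The plan's figures hold approximately as arithmetic for a two-outcome variable.

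**Step 2: admit a stable share.** Three ways of counting stable subjects are open.

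(a) *Stable or improving, all subjects, against 0.5.* The no-effect value is (1−s)/2 + s = 0.5 + s/2.

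| s | No-effect value | Chance of rejecting, n=90 | Chance of rejecting, n=45 |
|---|---|---|---|
| 10% | 0.55 | 15% | 8% |
| 20% | 0.60 | 46% | 23% |
| 30% | 0.65 | 81% | 48% |

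These are exact two-sided rejection probabilities, almost all in the upper tail. At n=45 the exact test rejects at 30 or more, or 15 or fewer. The n=45 column stands for one arm, if allocation is equal (an assumption) and 90 remain. At s=30% the no-effect value is exactly the 0.65 that the plan is powered to detect.

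(b) *Improving alone, all subjects, against 0.5.* The no-effect value is (1−s)/2: 0.45, 0.40 and 0.35. By symmetry the rejection rates are those in the table, but in the direction of too few improving.

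(c) *Changers only, against 0.5.* The null of 0.5 is valid under the symmetry assumption, but n becomes 90 × (1−s).

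- s=20%: n=72, z = (√72 × 0.15 − 0.980)/0.477 = (1.273 − 0.980)/0.477 = 0.61, power 0.73 (exact 0.72).
- s=30%: n=63, z = (√63 × 0.15 − 0.980)/0.477 = (1.191 − 0.980)/0.477 = 0.44, power 0.67 (exact 0.65).

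**Step 3: drift.** Under reading (c), 0.5 also needs improvement and worsening to be equally likely without the app. If 55% or 60% of changers improved for other reasons, upward rejection at n=90 would be 14% or 46%. These values are illustrations only; the documents give neither the direction nor the size of any drift.

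**The case against.** The strongest reply is that the plan never says it will test the stable-or-improving share against 0.5. The sentence naming that share leads into a precision statement, and the test sentence refers to improving or degrading. Read as a sign test among subjects who changed, 0.5 is a correct null. This stands, and it makes reading (a) conditional. It does not rescue the stated power, because a sign test among changers does not have 90 subjects once anyone is stable.

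A second reply is that a trajectory with balanced upward and downward steps is itself the stable one, so 0.5 describes stability. Other parts of the protocol do speak of decreases and increases in scores. The wording allows this, but the power figures count subjects, not steps, and steps with no change would raise the same counting question.

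Three stronger readings are tempting and are not supported:

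- *That an ineffective app will be declared successful.* No success rule rests on 0.5, and section C already states between-arm hypotheses that this problem does not touch.
- *That the illness course, described as "recurrent, often dramatic mood changes", by itself invalidates 0.5.* Symmetric fluctuation leaves improvement and worsening equally likely. Only a net drift would break it. People entering symptomatic and people entering remitted would tend to drift in opposite directions, and the documents give no net figure.
- *That the KIOS Analytics metrics carry the same error.* The plan says "Changes in the symptom scores provide a global measure of efficacy", which is loose wording for uncontrolled change. But no 0.5 appears there, and the formulas are left to a Phase I report that is not part of the documents.

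**Conclusion.** The point holds in a limited form. As written, the 0.5 null and the 0.80 power cannot both apply to 90 subjects if any of them is stable. With all subjects in the denominator the null value is wrong. With changers only, power for 0.65 is about 0.73 at 20% stable and 0.67 at 30% stable, not 0.80.

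The false-positive rates of 15%, 46% and 81% (n=90), or 8%, 23% and 48% (n=45), apply only if the stable-or-improving share is tested against 0.5. They also rest on the assumed stable shares and on symmetry.

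Separately, a within-subject test pooled over both arms can show change over time but cannot attribute it to either app.

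This should be fixed before analysis. Confidence is medium, because the text leaves the intended test open.

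**What to change.** 1. Do not use 0.5 as the reference for stable-or-improving.
2. Define improved, stable and worsened on BISS-42 or BISS-Self, which Table 1 schedules from week 0 to week 52 and which are collected in both arms. State the time points and the denominator.
3. Compare the three-category distribution between the randomised arms, adjusting for the week-0 score, in line with section C, and state the power of that comparison.
4. If the 0.5 test is kept, restrict it to subjects who changed, restate its power over a range of stable shares, and report it as descriptive change over time, not as app efficacy.

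**Cost.** No new data are needed; only the analysis text changes. The power becomes less favourable. As a rough guide, take 45 per arm (equal allocation assumed) and a simple two-proportion test on the stable-or-improving share. From 0.65 in one arm, 0.80 power needs about 0.89 in the other: (0.244 − 1.96 × √(2 × 0.772 × 0.228/45))/√(0.65 × 0.35/45 + 0.894 × 0.106/45) = (0.244 − 0.173)/0.085 ≈ 0.84. In return, the comparison keeps its error rate whatever the stable share: with equal true rates in two arms of 45, simulated two-sided error was 0.049 to 0.054 for stable shares of 20% to 50%.

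### Two different outcomes are called primary, and no KIOS-Bipolar versus eMoods comparison is designated to decide the trial

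*Combined protocol and SAP*

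**What the plan says.** The Plan of analysis (combined protocol and SAP, under ASSESS KIOS-BIPOLAR OR eMOODS) opens with "The primary aims of the analyses are to investigate patterns of adherence and attrition". It lists several usage indicators for adherence: "the proportion of weeks completed on time, the proportion completed only with follow-up prompts, and the number of weeks not submitted". Later in the same paragraph it states "Proportions of stable trajectories or improving trajectories are of primary interest".

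Section C, Hypotheses, lists a to g without ranking them. Hypothesis a predicts that the KIOS-Bipolar group "will have a higher proportion of time in remitted status, lower proportion in syndromal status (Manic, depressed, mixed) and higher" LFQ scores. Hypothesis b, on adherence, predicts the opposite kind of result: "Persistence with use of KIOS- Bipolar and eMoods will not differ". Hypothesis e adds another superiority claim, "LFQ subscales will be associated with superior outcomes for the KIOS-Bipolar group". Hypotheses f and g add directional claims about correlations with the BISS and about aggregate item changes.

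A significance level appears once, in a power statement that begins "For any hypothesis test for a proportion improving or degrading". It gives 0.80 power at two-tailed 0.05 to distinguish 0.65 from 0.5 with 90 subjects.

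**The concern.** The title and summary present a randomised comparative effectiveness study. A reader therefore expects one between-arm comparison whose result answers the question. The plan instead offers three candidates: adherence and attrition, trajectory proportions, and the three parts of hypothesis a. Nothing says which one governs.

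The candidates can also disagree. The trajectory test sets a proportion against 0.5, with each subject as their own control, so it could succeed without using the randomisation at all while every part of hypothesis a fails. Adherence is predicted not to differ, so a small p-value there would not be a success. At stake is whether the trial's headline is fixed in advance or picked from whatever turns out favourable.

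**Working it through.** **1. The plan's own power figure.** Inputs from the Plan of analysis: n=90, 0.65 against 0.5, two-sided 0.05.
- Normal approximation with null variance: (0.15 − 1.96 × 0.5/√90) / √(0.65 × 0.35/90) = (0.15 − 0.1033)/0.0503 = 0.929, giving power 0.824.
- Exact binomial (reject at 55 or more of 90, or the mirror image; actual size 0.045): 0.812. Continuity-corrected: 0.793.

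The stated 0.80 reproduces, and it is a one-sample figure.

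**2. It does not carry over to a between-arm test.** As an illustration only, compare 0.65 with 0.5 between two equal arms at two-sided 0.05, with a pooled-variance normal test.
- 45 per arm (90 subjects): (0.15 − 1.96 × √(2 × 0.575 × 0.425/45)) / √((0.25 + 0.2275)/45) = (0.15 − 0.2043)/0.1030 = −0.527, giving power 0.30.
- 60 per arm (all 120): 0.38.

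**3. Error rate if any part of hypothesis a counts.** Inputs: three outcomes (section C, a); two-sided 0.05, which is assumed because no level is stated for this hypothesis; one test per outcome. The documents give no correlations, so a range is shown. The independent column uses 1 − 0.95³ = 0.143 for either direction and 1 − 0.975³ = 0.073 for results favouring KIOS-Bipolar. The other columns come from simulating equicorrelated normal statistics (400,000 draws).

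| Correlation | 0 | 0.5 | 0.7 | 0.9 |
|---|---|---|---|---|
| At least one p<0.05, either direction (nominal 5%) | 14.3% | 12.6% | 10.9% | 8.3% |
| At least one favouring KIOS-Bipolar (nominal 2.5%) | 7.3% | 6.3% | 5.5% | 4.1% |

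Time remitted and time syndromal are shares of the same total, so independence is an upper end. If all three parts had to succeed there would be no inflation, but the plan does not say that either.

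**4. Adding the trajectory proportion as a fourth test.** 1 − 0.95⁴ = 18.6% if independent, 15.6% at correlation 0.5. Counting only favourable results, about 10% and 8%.

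**The case against.** The strongest reply is that the inflation is modest and easily exaggerated. Much of that stands. Three stronger readings are tempting, and the documents do not support them.

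- **That 0.05 is declared for every test.** The sentence is limited to proportions improving or degrading, tested against 0.5. No level is stated for hypothesis a or for hypotheses e to g. That is a gap, not a blanket rule.
- **That dozens of tests make a chance success likely.** Hypothesis g speaks of aggregate changes, not eight separate item tests. Objective f and the text below Table 1 confine eMoods comparisons to what that product can support. The number of LFQ subscales is not given, and hypothesis f concerns agreement between instruments rather than patient benefit. With independent tests, the chance of at least one p<0.05 in either direction passes one half only at 14 tests (1 − 0.95¹⁴ = 0.512), and the documents do not fix such a count.
- **That significance is tested weekly.** The section Outcome Measures from KIOS Analytics lets change be computed "either over the course of the entire field trial or at each incremental assessment", but it specifies no test and no between-arm comparison.

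It can also be said that the plan gives a precision for the difference between two subgroups, which could be applied to the arms. It does not tie that precision to the arms or to any outcome in hypothesis a. On the same normal basis, the 95% half-width at 45 per group is 1.96 × √(2 × 0.25/45) = 0.207, wider than the 0.15 departure on which the one-sample power rests.

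None of this supplies a deciding comparison. That gap does not depend on any error-rate figure.

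**Conclusion.** The point holds and should be settled before analysis. Two different things are called primary, the leading hypothesis concerns three others, and no between-arm result is designated to decide the trial. The stated power is arithmetically sound but answers a within-subject question.

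For hypothesis a alone, reading any one part as success raises the either-direction error from 5% to about 11–14%, and the error favouring KIOS-Bipolar from 2.5% to about 5.5–7.3%. This assumes one test per outcome, a level of 0.05 and correlations from 0 to 0.7. The error grows if hypotheses e to g are also treated as confirmatory, but the documents do not fix how many tests that means, so no figure is given. A reader might infer that a false success is more likely than not; the text does not support that.

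**What to change.** - Designate one primary between-arm comparison, with its test, at two-sided 0.05. Analyse it as randomised, since the protocol lets participants with technical problems switch group. Proportion of post-baseline time in remission is the natural candidate, because time in clinical states is objective a and remission comes first in hypothesis a. The choice is the sponsor's.
- Test the remaining parts of hypothesis a in a stated order, each at 0.05 only if the one before succeeded.
- Report hypotheses e, f and g, the one-sample trajectory proportions and the KIOS analytics as estimates with 95% intervals and no claim of success.
- Reword the two sentences on what is primary so that they agree with this.
- If remission time is chosen, define remission on the BISS-42 and state how the six scheduled post-baseline visits (weeks 8, 16, 24, 32, 40 and 52) become a proportion of time.
- Give between-arm power or precision for the chosen comparison.

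**Cost.** No added visits or data, and the fixed order splits no alpha. By contrast, an equal Bonferroni split over three tests (0.0167 each) would cut the illustrative two-arm power at 45 per arm from 0.30 to 0.17. It is more than a wording change: the outcome definition and the power statement must be written. Fewer results can be claimed as confirmed, and the stated one-sample power will no longer describe the primary test.
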